- Rate of stillbirth, defined as non-deliberate fetal death anytime in gestation at or after 19 completed weeks post-LMP
- Rate of premature delivery, defined as live birth prior to < 37 completed weeks gestation as counted from LMP
- Infant Outcomes
 - Rate and pattern of > 3 minor structural **birth** defects, where a minor structural **birth** defect is defined as a structural anomaly which has neither cosmetic nor functional significance to the child (itemized on the study examination form), and a pattern is defined as the same 3 or more minor malformations in 2 or more children
 - Rate of small for gestational age, defined as birth size (weight, length, or head circumference) < 10th centile for sex and gestational age using standard pediatric CDC growth curves for full term or preterm infants
 - Rate of postnatal growth deficiency, defined as postnatal size (weight, length, or head circumference) < 10th centile for sex and age using standard pediatric growth curves, and adjusted for postnatal age for premature infants if the postnatal measurement is obtained at < 1 year of age
 - Rate of postnatal serious infections and hospitalizations, as assessed throughout the 5-year postnatal follow-up period via pediatric records
 - Rate of infant reactions to scheduled vaccinations, as assessed throughout the 5-year postnatal follow-up period via pediatric records and a questionnaire designed to collect this information
 - Adequacy of immune response, as defined by an immunoglobulin (Ig)G-tetanus antibody assessment performed in the child between 6-12 months of age
 - Rate of adverse neurodevelopmental outcomes, as assessed in the child during 2 periods (between 16 months and 17 months 30 days of age and between 3.5-5 years of age) via standardized tests of performance
- Breastfeeding/Lactation Outcomes
 - Proportion of women who report breastfeeding (at all) in the first 6 weeks post-delivery; among women who breastfed in the first 6 weeks post-delivery, the proportion who breastfed exclusively for 2 weeks (both assessed via questionnaire administered between 0 – 6 weeks post-partum)

Exposure Variable(s)

The period defining exposure to evolocumab during pregnancy will be any number of days, at any dose, and at any time from the first day of the LMP up to and including the end of pregnancy. The period defining non-exposure to evolocumab during pregnancy will be no exposure any time within 90 days prior to the first day of the LMP.

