9.4.5.2 Phase II – Face-to-Face Developmental Testing at 3.5-5.0 Years of Age

When the children are at least 3.5 years of age but not yet 5.0 years of age, a subset will then be evaluated through a single set of direct assessments completed in the **subject's/child's** home setting, as well as an age appropriate set of maternally completed questionnaires. Preference will be given to the assessment of children exposed prenatally for the longest durations and children in each of the comparison groups who are of similar age. Longer duration exposures should improve the ability to assess risks because brain development continues throughout prenatal development and may be vulnerable to drug exposure beyond the first trimester. Direct assessment will be conducted using the Wechsler Preschool and Primary Scale of Intelligence-IV (WPPSI-IV). This standardized (Z-score), norm-referenced measure provides an evaluation of the child's general mental ability, verbal and non-verbal abilities, as well as

processing speed. The mother or primary caregiver will complete 1 questionnaire about the child’s development, the Behavioral Assessment Scale for Children (BASC-III), and questionnaires about her own functioning, the **CES-D**, the **PSI**, and the **Edinburgh Postnatal Depression Scale (EDPS)**. These questionnaires will provide additional information about the child’s social and emotional development in the family context. Additionally, a direct evaluation of the mother or primary caregiver’s cognitive functioning will be made using the Wechsler Abbreviated Scale of Intelligence (WASI-II). Understanding the cognitive level of the mother will facilitate accuracy of interpretation of children’s scores and any group differences.

Face-to-face assessments will be made until a sample size of 40/group (cohorts 1-3) has been reached. At this sample size, statistical power (0.80) will allow confidence in judgments of group differences of SD in primary score endpoints.

Table 2. Postnatal Developmental Screening and Evaluation, Phase I (16 Months and 17 Months 30 Days of Age) & Phase II (3.5-5.0 Years)

Age	Measure	Description

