9.5 Study Size

An enrollment total of 75 in the exposed group and 150 in each of the 2 comparison groups after 10 years is anticipated. Given that these numbers assume the prevalence of exposure is sufficient to support recruitment of these numbers, the feasibility of achievement will be re-evaluated at each annual interim review of the data.

Based on previous experience with MotherToBaby/OTIS Pregnancy Studies, we estimate that subjects will be an average of 7-10 weeks post-LMP at the time of enrollment. Given this mean gestational timing at enrollment, the anticipated spontaneous abortion/stillbirth rate is 10%, the estimated elective abortion rate is 5%, and the estimated lost to follow-up rate is 5%. This results in an estimated 71 observable pregnancies of which 60 are estimated to result in live births in cohort 1 (exposed group), and an estimated 142 observable pregnancies of which 120 are estimated to result in live births in cohorts 2 and 3 (control groups).

Baseline rates of major structural **birth** defects, spontaneous abortion, premature delivery, and small for gestational age, as well as the standard deviation for mean birth weight of full-term infants were based on previous MotherToBaby/OTIS studies and on general population data (Table 3). With the sample size estimated above, at $\geq 80\%$ power, alpha of 0.05, two-tailed tests of significance (except as noted below for pattern of minor structural **birth** defects), and each comparison group independently compared to the exposed group, the minimum effect sizes detailed in Table 3 will be detectable.

With respect to the evaluation of minor malformations, the strength of this study design is in the ability to examine the data for a pattern of minor and/or major structural **birth** defects, given that the known human teratogens are typically associated with a pattern as opposed to isolated major **structural** birth defects. A baseline prevalence estimate of 1% has been used for a specific pattern of minor **structural birth** defects. The RR detectable with this sample size is 10.0. This represents a 10% birth prevalence of a specific pattern (ie, approximately 6 children in the exposed sample), which is comparable to the birth prevalence of a specific pattern in other known human teratogens of moderate risk such as the anticonvulsant medications.

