9.7.2.4.1 Description of Study Enrollment

Outcome	Analysis Subset
Major Structural Birth Defect Among Live Births	All pregnancies ending in at least 1 live born infant
Major Structural Birth Defects Among All Pregnancies Excluding Lost to Follow-Up	All pregnancies excluding lost to follow-up
Spontaneous Abortion	Pregnancies enrolled prior to 20 weeks' gestation
Stillbirth	Pregnancies enrolled excluding lost to follow-up
Preterm Delivery	Pregnancies enrolled prior to 37 completed weeks' gestation, excluding pregnancies ending in twin or higher order multiple births
Minor Structural Birth Defects	Live born infants who have received the dysmorphology examination
Small for Gestational Age Infants	Live born infants excluding twin or higher order multiple births
Breastfeeding	Pregnancies ending in at least 1 live born infant
Postnatal Growth	Live born infants followed up to 1 year postpartum, excluding twin or higher order multiple births
Serious or Opportunistic Infections	Live born infants followed up to 1 year postpartum
Immune Function	Live born infants who received the tetanus titer testing
Response to vaccines	Live born infants who received at least one vaccine
Neurodevelopment	Live born infants for whom developmental screening questionnaires were completed or face-to-face testing was completed

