9.7.2.5.2 Secondary Analysis

The following will comprise the secondary analyses:

1. Comparison of all secondary outcomes between the Specific Evolocumab-Exposed cohort and Comparison Group I
2. Comparison of the primary and all secondary outcomes between the Specific Evolocumab-Exposed cohort and Comparison Group II

The comparison of the prevalence of the total proportion of major structural **birth** defects between the Specific Evolocumab-Exposed cohort and Comparison Group II will be among all live births and, separately, among all pregnancies excluding those lost to follow-up. The comparison of the prevalence of ≥ 3 minor malformations between the Specific Evolocumab-Exposed cohort and each of the 2 comparison groups will be among children who receive the dysmorphological examination. The comparison of IgG-tetanus antibody status (test negative or indeterminate vs test positive) by group (Exposed, Comparison Group I, Comparison Group II) among those in the biological sample sub-study.

In each cohort we will separately calculate the proportion of all pregnancies ending in live birth, spontaneous abortion, stillbirth, elective termination, and lost to follow-up; crude comparisons will be made between cohorts.

The evaluation for a pattern of minor structural **birth** defects will be conducted using the following steps:

1. A comparison among groups of the proportion of infants with any 3 or more minor structural **birth** defects will be made without regard to pattern
2. Among infants with 3 or more minor **structural birth** defects, the Evolocumab-Exposed group will be examined for evidence of a specific pattern of 3 or more defects in any 2 or more children. If such a pattern is identified, Comparison Groups I and II will be evaluated for any evidence of the same pattern.

In each cohort among all live born infants we will separately calculate the proportion of premature delivery, small for gestational age on weight, length or head circumference, and rates of serious infections, hospitalizations, adverse vaccine reactions, and adverse neurodevelopmental outcomes; crude comparisons will be made between cohorts.

Mean birth weight, length and head circumference for full-term live born infants will be compared between cohorts. Postnatal growth parameters will be compared using the proportion of infants ≤ 10 th centile for sex and age with respect to weight, height, or head circumference.

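### Two sections give conflicting denominators for adverse neurodevelopmental outcomes, and neither is the set of children tested in Phase II, so a Phase II rate could show a spurious relative risk of up to about 2

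*Protocol*

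**What the plan says.** The Abstract (Section 4) lists the outcome as "Rate of adverse neurodevelopmental outcomes, as assessed in the child during 2 periods", and Section 9.3.2.2.2 describes the same two periods.

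- **Phase I** (Section 9.4.5.1): questionnaires are requested from all mothers or caregivers in the three study groups.
- **Phase II** (Section 9.4.5.2): only a subset is tested. "Face-to-face assessments will be made until a sample size of 40/group (cohorts 1-3) has been reached".
- **Expected group sizes** (Section 9.5): "An enrollment total of 75 in the exposed group and 150 in each of the 2 comparison groups after 10 years is anticipated". This leads to 60 expected live births in the exposed cohort. In each comparison group it leads to "an estimated 142 observable pregnancies of which 120 are estimated to result in live births".

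Two denominators are then given for the neurodevelopmental outcome.

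- **Section 9.7.2.4.1**, analysis-subset table: "Live born infants for whom developmental screening questionnaires were completed or face-to-face testing was completed".
- **Section 9.7.2.5.2**: "In each cohort among all live born infants we will separately calculate the proportion of premature delivery". The same sentence goes on to several other outcomes, adverse neurodevelopmental outcomes among them, and announces crude comparisons between cohorts.

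Table 3 in Section 9.5 has a separate Phase II row. It is sized on 40 v 40 children as a continuous difference of 0.5 SD, not as a rate.

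**The concern.** The two sections contradict each other on who is counted. Neither gives a Phase II rate the denominator it needs, namely the children who had the face-to-face test. The protocol does this correctly for other outcomes that depend on an examination: minor defects are counted only among infants who had the dysmorphology examination, and tetanus antibody status only among those sampled.

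The choice matters because the Phase II cap is the same number in every group while the groups differ in size by a factor of two. A child who was not tested cannot be found adverse. Dividing by a set that includes untested children therefore dilutes the comparison rate more than the exposed rate. The result would be an apparent excess in exposed children that comes from testing coverage alone. Section 9.7.2.1 plans tests at 0.05 without multiplicity adjustment, so such an excess could be reported as a signal on a long-term child-safety outcome.

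**Working it through.** **Inputs.** From Section 9.5: enrollment of 75 exposed and 150 per comparison group; 10% spontaneous abortion or stillbirth, 5% elective abortion, 5% lost to follow-up; expected live births of 60 and 120. From Section 9.4.5.2: 40 tested per group. The protocol gives no Phase I completion rate and no adverse rate for either phase, so those below are assumed.

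**Step 1. Reproduce the live births.** 75 × 0.95 × 0.85 = 60.6 and 150 × 0.95 × 0.85 = 121.1. Taking 80% of those enrolled gives 60 and 120. The protocol's figures reproduce.

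**Step 2. Phase II coverage.** Exposed f = 40/60 = 0.667; comparison f = 40/120 = 0.333; ratio 2.0.

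**Step 3. Phase II rate over all live births.** Let the true adverse rate be p in both groups, with untested children in the denominator but not the numerator. The observed rate is f × p, so the null relative risk is 0.667p / 0.333p = 2.0 for any p. At p = 10%: 4/60 = 6.7% against 4/120 = 3.3%.

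Exact enumeration of a two-sided Fisher test at 0.05, with no true difference, gives these false-positive rates:

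| True rate p | Denominators 60 v 120 | Denominators 40 v 40 (tested) |
|---|---|---|
| 10% | 15.2% | 1.7% |
| 15% | 20.3% | 2.5% |
| 20% | 25.8% | 2.8% |
| 30% | 39.7% | 2.8% |

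With the tested children as denominator the null relative risk is 1.0.

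**Step 4. Phase II rate over the either-assessment set, read as one pooled set.** Let c be the Phase I completion proportion, equal in all groups and independent of Phase II testing (assumed). The share of live births in the set is 1 − (1 − c)(1 − f), and the observed Phase II rate is f × p / [1 − (1 − c)(1 − f)]. At p = 10%:

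| c | Exposed | Comparison | Null RR |
|---|---|---|---|
| 100% | 6.7% | 3.3% | 2.00 |
| 80% | 7.1% | 3.8% | 1.86 |
| 60% | 7.7% | 4.5% | 1.69 |
| 40% | 8.3% | 5.6% | 1.50 |

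**Step 5. A pooled any-phase rate, if one were formed.** Let q be the Phase I flag rate, with the phases independent (assumed). The numerator is 1 − (1 − cq)(1 − fp). The denominator is 1 for all live births, or as in step 4 for the pooled set. At p = 10%:

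| c | q | RR, all live births | RR, either-assessment set |
|---|---|---|---|
| 100% | 5% | 1.39 | 1.39 |
| 100% | 10% | 1.23 | 1.23 |
| 100% | 20% | 1.12 | 1.12 |
| 40% | 5% | 1.62 | 1.22 |
| 40% | 10% | 1.44 | 1.08 |
| 40% | 20% | 1.28 | 0.96 |

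On the either-assessment set the bias can nearly vanish, or reverse slightly.

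**The case against.** The best defence is that a sound reading is available. Section 9.9 plans no imputation of missing data, and counting untested children as unaffected would be a form of imputation. The all-live-born wording introduces a list of several outcomes, and the subset table narrows others in that list too, for example by excluding multiple births for small for gestational age. The table could therefore be taken to govern. Its *or* could be read per instrument: questionnaire completers for Phase I, face-to-face completers for Phase II. Finally, Table 3 already treats Phase II as a mean-score comparison of 40 v 40 tested children, and coverage does not bias that.

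Most of this stands. The mean-score comparison is not touched by the denominator problem, and the biased analysis is one that the text permits rather than one that it spells out. But no section says that the table overrides Section 9.7.2.5.2 or that the *or* is per instrument, and no section gives a Phase II rate its own denominator. Defining what is adverse on each instrument can be left to a statistical analysis plan. Two conflicting rules already stated in the protocol are a different matter.

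A reader might infer three stronger things that the documents do not support.

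- *The exposed rate is inflated.* It is not: at a true 10% it would appear as 6.7%. Only the ratio is inflated.
- *The protocol plans a single ever-adverse composite.* It describes assessment in two periods and nowhere says that a child counts once if flagged in either.
- *Preferring the longest-exposed children for Phase II adds to the denominator bias.* That choice is disclosed and reasoned in Section 9.4.5.2 and has no bearing on the denominator.

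**Conclusion.** The conflict between Sections 9.7.2.4.1 and 9.7.2.5.2 is real and should be resolved. If a binary Phase II rate is taken over all live births, the null relative risk is about 2.0 whatever the true rate, because coverage is 67% against 33%. Over the either-assessment set read as pooled, it is 2.0 at full Phase I completion and about 1.5 at an assumed 40%. For a pooled any-phase rate the size depends on Phase I completion and flag rates that the protocol does not give. On the either-assessment set that bias may be close to nil.

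The 67% and 33% are planning values. Section 9.2.2 continues recruitment for 10 years even if 75 exposed is reached, so the actual fractions will move. The imbalance remains while the comparison groups are about twice the exposed cohort and each group is tested up to the same cap. It would be wrong to conclude that the registry is bound to report a doubled risk: that requires a binary Phase II rate over the wrong denominator, which the text allows but does not compel.

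**What to change.** Make two edits and add one sentence.

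1. In Section 9.7.2.5.2, remove adverse neurodevelopmental outcomes from the sentence on proportions among all live born infants.
2. In Section 9.7.2.4.1, split the neurodevelopment row in two: Phase I outcomes among children with completed questionnaires, and Phase II outcomes among children with completed face-to-face testing.
3. State that the phases are reported separately and not pooled into one rate.

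The statistical analysis plan, if there is one, should carry the same two denominators. The cost is a few lines of wording. It needs no new data and does not change the Phase II sample or the mean-score comparison.

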9.7.2.4.2 Description of Subject Characteristics

Not applicable

9.7.2.5 Analysis of the Primary, Secondary, and Exploratory Endpoint(s)

9.7.2.5.1 Primary Analysis

Comparison of the primary outcome between the Specific Evolocumab-Exposed cohort and Comparison Group I will serve as the primary analysis.

Comparison of the prevalence of major structural **birth** defects between the Specific Evolocumab-Exposed cohort and Comparison Group I will be among all live births and, separately, among all pregnancies excluding those lost to follow-up.

Outcomes that are adjudicated as not associated with drug exposure will be excluded from the primary analysis, but included in a sensitivity analysis ([Section 9.7.2.6](#)).

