9.4.3 Outcome Interview

At any of the interim interview points, if the pregnancy has ended, the outcome interview will be conducted at this time or at the earliest convenient time for the mother (see [Appendix A](#), 05.G. Adverse Outcome Delivery and Birth Form or 02.F. Outcome Delivery and Birth Interview Form). For women who are still pregnant at the 32-34 week interview, the outcome interview will be conducted within 0 to 6 weeks after the expected due date (see [Appendix A](#), 02.F. Outcome Delivery and Birth Interview Form).

The outcome interview for live born infants will be a structured telephone interview and information will be elicited on the following: date of delivery, hospital location and mode of delivery; ethnicity, sex, birth weight, length and head circumference; Apgar scores; description of delivery or birth complications including malformations; type and length of hospital stay for mother and infant; delivering physician's and infant physician's names

and addresses; method of infant feeding; pregnancy weight gain; and additional exposures and results of prenatal tests occurring since the previous interview.

The outcome interview for spontaneous or elective abortions will also be structured and information will be elicited on the following: date and type of outcome; hospital location if applicable; prenatal diagnosis; pathology results if available; and additional exposures and results of prenatal tests occurring since the previous interview. The outcome interview for stillborn infants will include all of the above plus information on sex, birth size, and autopsy results, if available.

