a variety of factors which may be related to exposure and to pregnancy outcome, such as maternal cholesterol levels and comorbidities including cardiovascular disease history, obesity, diabetes, and hypertension. The use of a disease-matched comparison group addresses to some extent the issue of confounding by indication.

Misclassification bias due to poor recall is thought to be reduced in prospective study designs such as this. In addition, each subject is interviewed at several predetermined intervals during pregnancy. Misclassification bias regarding outcome is minimized in this study design through the use of a specialized physical examination and a standardized evaluation protocol.

Another strength of the study design is the anticipated minimal lost to follow-up rate. Based on previous experience of the investigators in the MotherToBaby/OTIS Pregnancy Studies, and the frequent subject contact, lost to follow-up is typically < 5% and therefore is not expected to pose a threat to the validity of study results. A subject meeting the criteria for enrollment is considered “lost to follow-up” if follow-up information on the outcome (live birth, fetal loss) is not obtainable, or for a live birth if the birth defect status is designated as “unknown” as of 12 months following the estimated due date. Before a **subject** is designated as lost to follow-up, the subject or reporter receives at least 3 reminder telephone calls (documented in database) followed by written correspondence; alternative contact information that is requested upon enrollment is also utilized. All follow-up attempts are documented. Losses to follow-up are tallied in the Registry Interim Reports. No imputation of missing data is planned.

Finally, the primary strength of the cohort study portion of the Registry is its sensitivity for detection of a pattern of malformation. As the known teratogens are associated with specific patterns of malformation, this study design, by virtue of providing study-related dysmorphological evaluation of prospectively ascertained and exposed infants, has the unique capability of detecting within reasonable limits such a pattern if it exists.

10. Protection of Human Subjects

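### In the all-pregnancies version of the primary analysis, losses and terminations with unknown defect status stay in the denominator, while live births with unknown status are removed

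*Protocol*

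**What the plan says.** Section 9.7.2.5.1 of the protocol sets two denominators for the primary comparison with Comparison Group I. The comparison "will be among all live births and, separately, among all pregnancies excluding those lost to follow-up". The table in section 9.7.2.4.1 defines the second set as "All Pregnancies Excluding Lost to Follow-Up" and does not require defect status to be known. Section 9.7.2.5.2 uses the same pair of denominators against Comparison Group II.

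Section 9.9 says who is lost to follow-up. A subject is lost "if follow-up information on the outcome (live birth, fetal loss) is not obtainable, or for a live birth if the birth defect status" is unknown 12 months after the due date. The same paragraph adds: "No imputation of missing data is planned".

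On how defects are found, section 9.4.6 gives the study dysmorphology examination to live born infants. For abortions, section 9.4.3 asks about prenatal diagnosis and for "pathology results if available"; for stillbirths it adds autopsy results on the same condition. Section 9.4.4 sends release forms for such reports where they exist.

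On numbers, section 9.5 states that "the anticipated spontaneous abortion/stillbirth rate is 10%, the estimated elective abortion rate is 5" per cent, and: "This results in an estimated 71 observable pregnancies of which 60 are estimated to result in live births in cohort 1". The comparison groups have 142 and 120. Table 3 sizes the primary endpoint on 71 against 142, which is the all-pregnancies set.

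**The concern.** Unknown defect status is handled differently according to how the pregnancy ended. A live birth with unknown status leaves the analysis. A loss or termination with unknown status stays in, because its outcome is known and the defect-status clause in section 9.9 covers live births only. With no imputation, such a pregnancy adds one to the denominator and can add nothing to the numerator. The protocol never says that it is scored as unaffected, but a simple prevalence on this set has that effect.

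Pregnancy loss is itself a safety outcome of the registry. If exposure raised loss, more exposed pregnancies would move into the part of the denominator that cannot yield an event. The defect comparison would then look more reassuring because of a second harm. None of the analyses listed in section 9.7.2.6 tests for this. They deal with prenatal testing, gestational timing of enrolment, timing and length of exposure, and chromosomal or otherwise adjudicated outcomes. The subsection on residual confounding and bias is marked as not applicable.

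**Working it through.** **The plan's own figures.** Section 9.5 assumes 5% lost to follow-up, 10% spontaneous abortion or stillbirth, and 5% elective abortion.

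- Observable pregnancies: 75 × 0.95 = 71.25 and 150 × 0.95 = 142.5, stated as 71 and 142.
- Live births: 71 × (1 − 0.10 − 0.05) = 60.35 and 142 × 0.85 = 120.7, stated as 60 and 120. The figures reproduce.
- Pregnancies not ending in live birth: 71 − 60 = 11 and 142 − 120 = 22, or 15.5% of each. This is the ceiling for unassessed pregnancies. If half of the losses have usable reports, the share is 0.15 × 0.5 = 7.5%.

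**Dilution formula.** Let L be the proportion of followed pregnancies that end in loss or termination, and u the share of those with no defect information. Assume u is the same in both groups and defect risk is the same in lost and live-born conceptuses. The observed rate is then the true rate × (1 − uL), and

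observed RR = true RR × (1 − u·L_exposed) / (1 − u·L_comparison).

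The multiplier does not depend on the 4% baseline rate. The documents do not give u, so it is shown at 1 (no loss assessed) and at 0.5.

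**Equal loss.** With L = 0.15 in both groups the multiplier is 1 and the RR stays at 3.8. Only the rates fall: at u = 1, from 15.2% and 4.0% to 15.2% × 0.85 = 12.9% and 4.0% × 0.85 = 3.4%.

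**Higher loss in the exposed group** (comparison group at 15%, true RR 3.8):

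| Exposed loss | u = 1 | u = 0.5 |
|---|---|---|
| 20% | 3.8 × 0.80/0.85 = 3.58 | 3.8 × 0.90/0.925 = 3.70 |
| 25% | 3.8 × 0.75/0.85 = 3.35 | 3.8 × 0.875/0.925 = 3.59 |
| 30% | 3.8 × 0.70/0.85 = 3.13 | 3.8 × 0.85/0.925 = 3.49 |

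The 30% row uses Table 3's detectable RR for pregnancy loss: 2.5 × 10% = 25%, plus 5% terminations.

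**True RR of 1.0, exposed loss 30%.** The observed RR is 0.70/0.85 = 0.82 at u = 1 and 0.85/0.925 = 0.92 at u = 0.5.

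**The case against.** The strongest reply is that the protocol does look for defects in losses. It asks about prenatal diagnosis, pathology and autopsy, requests the reports, and updates prenatal test results at the interim interviews. Terminations that follow a diagnosed anomaly are among the losses most likely to have a record. This stands. A reader might infer that about 15% of pregnancies are scored as unaffected without assessment; the documents support 15% only as an upper bound.

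Second, the effect on the RR is conditional. It needs more loss in the exposed group, or a difference between cohorts in how losses are assessed, and the latter could move the RR either way. A loss RR of 2.5 would probably be noticed, since section 9.7.2.5.2 tabulates pregnancy outcomes by cohort and Table 3 claims 88% power for it. The live-birth version, reported alongside, is free of this dilution. All of this stands and limits the size of the problem. It does not remove it: seeing an excess of loss does not show how far the defect RR was diluted, and the live-birth version cannot see defects in pregnancies that did not reach live birth.

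Third, section 9.7.2.3 calls a pregnancy lost when outcome information cannot be obtained, which might be read to cover unknown defect status in a loss. Section 9.9 is more specific: it gives live birth and fetal loss as the outcome and adds the defect-status condition for live births only. The general wording does not undo that. A statistical analysis plan, not at hand, may settle the scoring, but the asymmetry is in the protocol's own text.

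A reader might also infer that this denominator costs the study power. That does not hold. With equal loss and no loss assessed, 71 against 142 at the diluted rates gives 69.0% (Fisher) or 72.5% (chi-square). Restricting to 60 against 120 at 15.2% and 4% gives 69.0% or 74.5%. The information is missing under either denominator. The comparison also assumes that 4% is a rate per assessable pregnancy, which the documents do not establish.

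**Conclusion.** The point holds as a gap in one of the two primary denominators. Section 9.9 treats unknown defect status differently for live births and for losses, so up to about 15% of pregnancies in the all-pregnancies set may be unable to count as events. The true share depends on how many losses have reports, which the documents do not say.

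With equal loss and equal assessment the RR is unbiased. At 30% against 15% total loss a true 3.8 becomes 3.13 to 3.49, and a true 1.0 becomes 0.82 to 0.92, for u from 1 to 0.5. These figures assume the same u in both groups and the same defect risk in lost and live-born conceptuses. Under those assumptions, excess exposed loss biases toward reassurance. The documents do not support the stronger conclusion that the primary RR is pulled down as the study is planned. This is a cheap improvement to a safety comparison, not a flaw that invalidates it.

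**What to change.** Keep both planned analyses and make three additions.

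1. Report, by cohort, the number of spontaneous abortions, terminations and stillbirths with known and with unknown defect status.
2. In section 9.7.2.6, add a sensitivity analysis of the all-pregnancies comparison restricted to pregnancies with known defect status. Losses and terminations then follow the same rule as live births, applied identically in every cohort.
3. Add a bounding analysis that gives unassessed losses the live-birth defect rate, and then a stated multiple of it.

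The cost is some wording and one extra table, drawn from reports the protocol already requests. The drawback is that investigated losses are a selected group, since some are investigated because a defect was suspected, possibly to a different extent in each cohort. The known-status analysis should therefore supplement the planned all-pregnancies analysis and not replace it; the bounding analysis shows how much the conclusion depends on the losses that were not assessed.
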